3.9 Summary of Background and Data on Linezolid

S. aureus bacteraemia remains a life-threatening condition with high morbidity and a mortality of up to 30% despite antibiotic therapy. Emerging evidence suggests that bacterial virulence factors significantly contribute to organ damage and poor patient outcomes. Linezolid, a well-established antibiotic with anti-virulence factor properties, offers a promising adjunctive treatment option. Preclinical studies demonstrate that linezolid effectively inhibits *S. aureus* virulence factor expression and improves survival in animal models. Clinical data support its safety and efficacy in various *S. aureus* infections, including pneumonia and bacteraemia.

Since its approval more than 20 years ago, the risk profile of linezolid has been well-documented. The approved treatment duration varies from 10-28 days depending on the cause and location of the infection. Notable adverse events of linezolid are myelosuppression, serotonin syndrome, kidney injury, *C. difficile*-associated diarrhoea, lactic acidosis, and neuropathy. Myelosuppression is typically associated with prolonged use (≥ 10 days) and is reversible upon linezolid discontinuation. Serotonin syndrome is very rare with monotherapy and remains uncommon even with concurrent serotonergic medications. Renal adverse effects including increased creatinine and rare cases of renal failure have been reported with linezolid use. Like many antibiotics, linezolid has been associated with *C. difficile*-associated diarrhoea, which can range from mild diarrhoea to fatal colitis. Lactic acidosis is rare but serious and is linked to extended treatment durations. Neuropathy has been described in patients with treatment durations exceeding the maximum recommendation of 28 days and is thus very unlikely to occur in this trial.

Since linezolid will be administered for only 5 days in the LIPS trial, a favourable safety profile is expected. In addition, hospitalization of study participants facilitates a close monitoring for any adverse events.

Given the significant unmet clinical need and the favourable safety profile of short-term linezolid therapy, the anticipated benefits — including reduction of virulence factor-mediated complications and improvement in patient-relevant outcomes — clearly outweigh the manageable risks. The trial will provide critical evidence on whether early adjunctive treatment with linezolid improves outcomes in *S. aureus* bacteraemia. If linezolid proves to be effective in treating *S. aureus* bacteraemia, it holds the potential to improve the therapeutic management of millions of patients with this condition worldwide.

4. STUDY OBJECTIVES

4.1 Overall Objective

The purpose of the LIPS trial is to evaluate whether the addition of linezolid to standard therapy in participants with *S. aureus* bacteraemia leads to an overall improvement in patient-related outcomes such as mortality, health-related quality of life, complications, and duration of hospitalisation.

4.2 Primary Objective

The primary objective is to investigate whether early addition of 5-day treatment with linezolid to standard of care improves outcomes at 90 days in participants with *S. aureus* bacteraemia as measured by the desirability of outcome ranking (DOOR).^{98 99}

4.3 Secondary Objectives

Secondary objectives include exploring the impact of early addition of 5-day treatment with linezolid to standard of care on a number of secondary outcomes such as physical and mental health, length of hospital stay (full list in section 5 STUDY OUTCOMES). In addition, we aim to explore if potential effects might differentiate between patient population based on sex (male vs. female), ICU status at baseline (participants on ICU vs. participants not on ICU), and focus of infection (vascular catheter, skin and soft tissue, endocarditis, osteoarticular, pneumonia, other focus, or focus not identified).

4.4 Safety Objectives

The LIPS study aims to assess the safety of early addition of 5-day treatment with linezolid to standard of care treatment for *S. aureus* bacteraemia in a real-world setting. Details on adverse events of special interests can be found in chapters 5.4 *Safety Outcomes* and 9.2.4 *Assessment of safety outcomes*.

5. STUDY OUTCOMES

5.1 Primary Outcome

The primary outcome utilises the Desirability of Outcome Ranking (DOOR), which has been specifically introduced as a patient-centred outcome for *S. aureus* bacteraemia.^{100 101} This hierarchical composite outcome ranking has the advantage that it can incorporate multiple outcomes (both beneficial and harmful) to measure if patients experience better overall outcomes after receiving a specific intervention compared with an appropriate comparator ("Good Studies Evaluate the Disease While Great Studies Evaluate the Patient"¹⁰⁰). In contrast to composite outcomes, the DOOR outcome does not have the limitation that events of different importance are weighted equally.¹⁰² We modified the proposed ranking based on the feedback of our patient representatives and the ongoing SNAP trial.¹⁰³ The most important outcome for patient representatives was surviving the infection. The second most important aspect was that they "are the same as before the disease", meaning that they have the same level of function as before the *S. aureus* infection. Patient representatives with a history of *S. aureus* bacteraemia informed us that results of their bacterial blood culture were of highest relevance to them during their hospital stay due to high uncertainty of the progression of the disease. This was particularly important because diagnostic evidence of persistent, relapsing or new *S. aureus* infection results in new diagnostic steps, interventions and/or new exposure to antibiotics with their accompanying toxicities. Therefore, we have implemented the third domain *complications*, including microbiological and clinical failure leading to treatment change, and serious adverse reactions or adverse events leading to study drug discontinuation. Finally, hospital length of stay was included as the fourth DOOR component, since patient representatives mentioned it as an important outcome. We will use outcome definitions consistent with the SNAP trial to facilitate data comparisons.

DOOR comprises five ranks (Table 3: Desirability of Outcome Ranking (DOOR) outcome used for the LIPS trial). This outcome is assessed at day 90. The overall distribution of rankings can then be compared between the control and intervention arms, with the final treatment effect estimate being the win ratio, i.e., the probability that a participant randomly assigned to the intervention arm has a superior DOOR compared to a participant randomly assigned to the control arm⁹⁹ (see section 11 STATISTICAL METHODS).

Rank	Alive at 90 days	Return to usual level of function by day 90	None of the following complications:	Hospital length of stay
1	Yes	Yes	Yes (no complications occurred)	Ties will be resolved using the length of hospitalisation
2	Yes	Yes	No (complication occurred)	
3	Yes	No	Yes (no complications occurred)	
4	Yes	No	No (complication occurred)	
5	No	Not applicable	Not applicable	Not applicable

Table 3: Desirability of Outcome Ranking (DOOR) outcome used for the LIPS trial

Detailed definitions of DOOR components:

Alive at 90 days: defined as alive at 90 days after randomisation

Return to usual level of function by day 90: defined as return to baseline value (or better score) according to the modified functional bloodstream infection score¹⁰⁴. Baseline is defined as the best score within the 4 weeks before randomisation. The scores used will be the following:

- 6: Out of hospital, able to complete daily activities without assistance (no limitations)
- 5: Out of hospital, able to complete daily activities without assistance but with some limitations (e.g. slow, pain)
- 4: Out of hospital, unable to complete daily activities without assistance
- 3: Out of hospital; significant disability; requires a high level of care and assistance daily (this includes residential

aged care and nursing homes)

2: Hospitalised (or equivalent)

1: On palliative care in terminal phases of life (in hospital or at home)

Complications:

- Microbiological or clinical failure leading to treatment change: This includes any type of adaptation of the treatment such as new intervention or surgery, or re-start, prolongation or change of antibiotic treatment
 - Microbiological failure: Any positive sterile site culture with *S. aureus* between 14 and 90 days after randomisation. A sterile site means any site of the body where microorganisms are usually absent, i.e. below the outer and inner colonised surfaces of the skin and mucous membranes. Positive sterile sites cultures include deep visceral and musculoskeletal abscesses obtained in a sterile manner.
 - Clinical failure: Newly identified focus of *S. aureus* between 14 and 90 days after randomisation as determined by the site investigator (or delegated physician). This can incorporate clinical, radiological, microbiological and pathological findings.
- Serious adverse reaction (SAR, see definition below)
- Any adverse event (irrespective of grade) leading to study drug discontinuation

Hospital length of stay: This corresponds to the duration of the index acute hospital stay from randomisation until the day of hospital discharge. Transfers to another acute care hospital for continuation of acute treatment will be included in the assessment of hospital length of stay. Days after transfer to rehabilitation centres or switch to outpatient parenteral ambulatory treatment will not be included in the acute hospital stay.

5.2 Secondary Outcomes

The secondary outcomes include each part of the DOOR outcome separately as well as additional patient-relevant outcomes and specific outcomes of interest to assess the influence on infection dynamic and control. The secondary outcomes have been aligned to the SNAP trial to allow comparison of the data at a later time point.

Separate parts of the DOOR outcome:

- All-cause mortality at 90 days
- Return to usual level of function at day 90
- Microbiological treatment failure 14-90 days after randomisation leading to treatment change
- Clinical treatment failure 14 and 90 days after randomisation leading to treatment change
- Length of hospital stay of acute index hospitalisation
- Adverse events leading to study drug discontinuation

Clinical outcomes:

- Time to death up to day 90
- Time to being discharged alive
- Number of days without being on the ICU up to day 90

Infection dynamics and control:

- Persistent bacteraemia: positive blood culture on day 5 (± 1 day) after randomisation
- Two or more systemic inflammatory response syndrome (SIRS) criteria on day 5 after randomisation
- Change in C-reactive protein (CRP) from day 1 until day 5 (± 1 day) after randomisation
- Early microbiological treatment failure 5-13 days after randomisation leading to treatment change
- Early clinical treatment failure 5-13 days after randomisation leading to treatment change

- Development of any new antibiotic drug resistance in *S. aureus* until day 90
- Number of days alive and free of antibiotics in the 90 days

Patient-reported outcomes:

- Physical health at day 90 as assessed by the short form 36 (SF-36) questionnaire.¹⁰⁵⁻¹⁰⁷
- Mental health at day 90 as assessed by the short form 36 (SF-36) questionnaire.¹⁰⁵⁻¹⁰⁷

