7.3 Assignment to study groups

Participants will be allocated 1:1 to either linezolid for 5 days or placebo for 5 days. The randomisation will be stratified by centre and ICU status at time of enrolment and done using block randomisation with varying random block sizes of 2 or 4. The trial statistician will generate the randomisation list outside of the data capture system REDCap®. This list will then be uploaded into the data capture system. The goal is to randomise participants such that the groups are as balanced as possible with respect to study centre and ICU status at time of enrolment.

After informed consent has been obtained and all eligibility criteria have been reviewed and met, the local investigator (or designated staff) enters the minimal required data into REDCap® (i.e., participant ID, year of birth, if participant is on ICU). The allocation is done by REDCap® which will display a unique, randomisation number that remains the same throughout the study. Each randomisation number will correspond to a drug container which is labelled with the unique randomisation number.

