9.3.4 Assessment of baseline characteristics (day 1)

Most study-specific baseline characteristics are assessed as part of the clinical routine and can be extracted from the patient charts of each centre. The baseline characteristics include date of hospital admission, index blood culture, linezolid susceptibility, ethnicity, vital signs, polymicrobial bacteraemia (defined as more than one organism [at species level] in the index blood cultures, excluding those organisms judged to be contaminants by the treating clinicians), comorbidities, standard antibiotic treatment, markers of severity (mechanical ventilation, cardiac arrest, use of vasopressors, ICU), labour force status, injection drug use, and mental health diagnosis. The data closest to the time before start of the study treatment should be used. The study team of each site will check at the time of randomisation if all relevant information is available from the clinical routine assessment and – if necessary – will add the missing information by contacting the treating team or the participant directly. Together with the participant, the local investigator (or a delegated physician) will assess the level of function 4 weeks before randomisation. In case the participant is not able to provide this information, this data will be assessed at day 90 (asking about their level of function 4 weeks before their *S. aureus* bacteraemia).

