9.3.18 Assessment of return to usual level of function (day 90 ±7)

During the phone call at day 90, the participant will be asked to rate their level of function in the 4 weeks prior to their bacteraemia and their current level of function from 6 to 1 according to the modified functional bloodstream infection score (see chapter 5.1 *Primary Outcome* for the corresponding scale). All levels of the scale will be presented orally in a clear and precise manner, ensuring that the participant has adequate time to self-assess. In the event of any misunderstanding regarding the classifications, the scale will be repeated as necessary. If the participant is unable to perform the self-assessment (whether due to medical reasons or limited communication abilities over the phone), efforts will be made to contact a family member or the participant’s primary care physician to obtain the information.

9.3.19 Assessment of physical and mental health (quality of life, SF-36, day 90 ±7)

Quality of life (i.e. mental health and physical health) will be assessed at day 90 through the SF-36 questionnaire. Participants will have the option to complete it either electronically or on paper. At the time of enrolment in the study, participants will be asked which method they prefer. For the electronic version, participants will be requested to provide their email address and/or mobile phone number. This information will be encrypted and accessible only to the local Investigator of the respective centre. On day 90, participants will be notified via email or mobile phone

message about the task and will be directed to the corresponding online version of the study-specific SF-36 questionnaire. For participants who prefer the written version, a letter with a printed version of the SF-36 questionnaire will be sent by postal mail, including an envelope for returning the filled questionnaire. We expect that participants will need approximately 10 minutes to complete the questionnaire. At the time of the 90-day telephone call, participants will be asked whether they have already completed the questionnaire and if they have any questions regarding it. It is not intended for the questionnaire to be filled out verbally over the phone, as this could potentially introduce bias.

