11.4.3 Secondary Analyses

We intend to conduct the following analyses for the secondary outcomes:

Logistic regression

- Returning to usual level of function by day 90
- Microbiological treatment failure 14-90 days after randomisation
- Early microbiological treatment failure 5-13 days after randomisation
- Clinical treatment failure 14-90 days after randomisation
- Persistent bacteraemia defined as positive blood culture on day 5 after randomisation
- Meeting two or more SIRS criteria simultaneously on day 5 after randomisation

Log-normal linear regression

- Length of hospital stay of acute index inpatient hospitalisation (in days)

Poisson regression

- Number of days without being on the Intensive Care Unit (ICU) up to day 90
- Number of days alive and free of antibiotics up to day 90

Cox proportional hazards model

- Time to death up to day 90

Fine & Gray competing risk model

- Time to being discharged alive (assessed until day 90)

The models listed above will include sex, ICU stay at baseline, and centre as adjustment factors (will be further pre-specified in separate data analysis plan).

Wilcoxon-Mann-Whitney test

- Physical health at day 90 as assessed by the short form 36 (SF-36) questionnaire
- Mental health at day 90 as assessed by the short form 36 (SF-36) questionnaire

Subgroup analyses: We will conduct the following subgroup analyses on the primary outcome to assess if treatment effects differ by sex (male vs. female), ICU status at baseline (participants on ICU vs. participants not on ICU), and dominant focus of infection (vascular catheter, skin and soft tissue, endocarditis, osteoarticular, pneumonia, other focus, or focus not identified).

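### The two SF-36 scores are the only secondary outcomes with a stated method that are compared without adjustment, at a small cost in precision and with no effect estimate named (minor)

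*Protocol*

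**What the plan says.** Section 5.2 lists "Physical health at day 90 as assessed by the short form 36 (SF-36) questionnaire" and the equivalent mental-health score under patient-reported outcomes. Section 9.3.19 sets the time point: "Quality of life (i.e. mental health and physical health) will be assessed at day 90 through the SF-36 questionnaire". The schedule in section 9.1 has no baseline SF-36.

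Section 11.4.3 groups secondary outcomes by method. It begins with logistic, log-normal linear, Poisson, Cox and Fine & Gray models, and then states: "The models listed above will include sex, ICU stay at baseline, and centre as adjustment factors", adding in brackets that this "will be further pre-specified in separate data analysis plan". Only after that comes the entry "Wilcoxon-Mann-Whitney test", which holds the two SF-36 outcomes and nothing else. No stratum, covariate or effect measure is named for them.

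On allocation, section 7.3 says: "The randomisation will be stratified by centre and ICU status at time of enrolment".

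**The concern.** The adjustment sentence points backwards, so the SF-36 scores fall outside it. They are then compared without the two stratification factors and without sex, while every other secondary outcome that 11.4.3 assigns to a method is adjusted for all three. If ICU status, centre or sex predicts day-90 quality of life, an unadjusted comparison after stratified allocation is slightly conservative and less precise than it could be. With no baseline SF-36, covariates already recorded are the only route to better precision.

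The named test by itself also gives a p-value and no size of effect. Section 4.1 puts health-related quality of life in the overall objective, section 6.2.1 records that the patient representatives advised a day-90 quality-of-life measure, and section 6.2.2 plans to discuss with them which effects matter. Those uses need an estimate with an interval.

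**Working it through.** **Order of the text.** In 11.4.3 the sequence is: five model types with their outcomes, the adjustment sentence, the Wilcoxon entry. Read in that order, the adjustment does not cover SF-36, and no other section supplies an adjusted or stratified SF-36 analysis.

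**Plan's own figure.** There is none: the protocol states no SF-36 standard deviation, target difference, completion rate or power. Its power statement concerns the win ratio only.

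**Inputs from the protocol (section 11.2).** 303 participants per arm; 90-day mortality 22.5% with control and 20.3% with linezolid; two-sided alpha 0.05.

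**Assumed inputs.** SD 10; true difference 3 points; completion among survivors 90%, with 70% as the low case; share of outcome variance explained by the covariates (R²) 0.02 to 0.20.

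**Respondents.** Survivors: 303 × (1 − 0.225) = 234.8 and 303 × (1 − 0.203) = 241.5, together 476.3. At 90% completion: 476.3 × 0.9 / 2 = 214 per arm. At 70%: 167 per arm.

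**Unadjusted Wilcoxon power.** Under normality its efficiency relative to the t-test is 3/π = 0.955, so the effective n is 214.3 × 0.955 = 204.7 per arm. Then z = (3/10) × √(204.7/2) = 3.035, and power = Φ(3.035 − 1.960) = 85.9%.

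**With adjustment.** The residual SD becomes 10 × √(1 − R²), so z is divided by √(1 − R²). At R² = 0.10: 3.035 / 0.949 = 3.199, and Φ(1.239) = 89.2%.

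| R² | CI width relative to unadjusted | Adjusted rank power, 90% completion | Linear regression power, 90% completion | Adjusted rank power, 70% completion |
|---|---|---|---|---|
| 0 | 1.000 | 85.9% | 87.4% | 76.3% |
| 0.02 | 0.990 | 86.6% | 88.0% | 77.1% |
| 0.05 | 0.975 | 87.6% | 89.0% | 78.4% |
| 0.10 | 0.949 | 89.2% | 90.6% | 80.5% |
| 0.20 | 0.894 | 92.4% | 93.5% | 84.9% |

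The gain from adjustment itself is read down the third column: 0.7, 1.7, 3.3 and 6.5 percentage points. The further 1.1 to 1.5 points in the regression column come from least squares beating ranks when the data are assumed normal. That is not a cost of ignoring the strata.

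**The case against.** The strongest reply is that nothing here is an error. An unadjusted Wilcoxon test is valid after stratified randomisation, and the secondary objectives are exploratory. Section 11.4.2 describes the primary win ratio without adjustment too, so an unadjusted rank comparison fits the trial's main analysis. Section 11.4.1 presents the analyses as current intentions ahead of a detailed plan, where covariates and effect measures for a secondary outcome would normally be settled.

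Most of this stands, and it is why the point is minor. What remains is that the protocol does name a method for these two outcomes. The deferral in 11.4.3 is attached to the adjustment factors of the preceding models, not to the Wilcoxon entry. An unspecified effect estimate would, taken alone, be a matter for the analysis plan.

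A reader might go further in three ways that the documents do not support:

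- That the comparison is biased or its error rate inflated. It is not; at most it is slightly conservative.
- That SF-36 is the only unadjusted analysis in the trial. The win ratio is also described without adjustment, and change in CRP, new resistance, early clinical failure and 90-day mortality as a proportion have no method in 11.4.3.
- That the loss is large. At an R² of 0.25, regression would carry (π/3) / (1 − 0.25) = 1.40 times the information of the unadjusted Wilcoxon test. About 4.7% of that is the least-squares factor π/3, and an R² that high would probably need age and prior function, which are outside the stated adjustment set.

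Prior function is also not a clean baseline covariate. Section 9.3.4 says "the local investigator (or a delegated physician) will assess the level of function 4 weeks before randomisation", but allows the question to be put at day 90 when the participant could not answer, and section 2.7 expects 10-20% of patients to be unable to consent during the acute infection.

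**Conclusion.** The point holds as a minor one about efficiency and reporting. Among secondary outcomes with a stated method, only the two SF-36 scores are compared without sex, ICU status and centre, two of which define the randomisation strata, and no effect estimate is specified for them.

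Under the assumptions shown, leaving out the adjustment costs about 1 to 3 percentage points of power at R² of 0.02 to 0.10 and about 7 at 0.20. Equivalently, the confidence interval is about 1 to 5% wider, or 12% wider at the top (1/0.894 = 1.118). If the covariates predict nothing, nothing is lost. The direction is secure if any of them is prognostic; the size rests on an SD, difference, completion rate and R² that the protocol does not give. With no baseline SF-36, the lower end is more likely for the stated adjustment set.

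**What to change.** In section 11.4.3, analyse each SF-36 component summary by linear regression on treatment with the set already used for the other models (sex, ICU status at baseline, centre), and report the adjusted mean difference with its 95% CI. Age may be added. The pre-infection function score should enter only where it was obtained at baseline, or in a sensitivity analysis.

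If a rank method is preferred, use a van Elteren test stratified by both ICU status and centre, pooling small centres, with a Hodges-Lehmann estimate and CI. Stratifying by ICU status alone would leave out one of the two randomisation factors.

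The cost is one line of wording; sex, ICU status and centre need no new data or visits. The downside is that a mean-difference model relies on large-sample normality, which is reasonable with several hundred respondents.

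The change leaves two matters open. About 21% of participants are expected to die before day 90 (1 − 476.3/606) and will have no score under either method. Section 9.2.2 also pairs physical health with the Mental Component Summary and mental health with the Physical one; this should be reconciled before the line is written.
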